7.9.6 Health-related quality of life (HRQoL)

HRQoL must be evaluated by the subject at Baseline, Week 4, Week 8, and Week 12 or Early Termination using the Skindex-10, 5D-Itch and EQ-5D-5L questionnaires.

7.9.6.1 Skindex-10

The Skindex-10 consists of 10 questions (beginning with "During the past week, how often have you been bothered by.....") exploring the impact of itch on 3 domains (disease, mood/emotional distress and social functioning) with a 1 week recall period.

Each question must be scored on a 7-point scale ranging from 0 (never bothered) to 6 (always bothered).

The domain scores are the sums of the following: disease domain (questions 1 to 3), mood/emotional distress domain (questions 4 to 6), and social functioning domain (questions 7 to 10).

The total score is the sum of the numeric value of each answered question. The total score ranges from 0 to 60.

7.9.6.2 5D-Itch

The 5D-Itch consists of 5 domains numbered 1-5. Domains 1-3 are single item (question) domains exploring the Duration (Duration domain), Degree (Degree domain) and Direction (Direction domain) of Itch. Domain 4 (Disability domain) includes four items (questions) assessing the impact of itching on daily activities: sleep, leisure/social activities, housework/errands and work/school). Domain 5 (Distribution domain) assesses the number of affected body parts out of 16 possible options. For each of domains 1-3 the domain score is equal to the value indicated below the response choice (range 1–5). For domain 4 the score is achieved by taking the highest score on any of the four items (range 1-5). For domain 5 the score is obtained by tallying the number of affected body parts and the sum is sorted into five scoring bins: sum of 0-2 = score of 1, sum of 3-5 = score of 2, sum of 6-10 = score of 3, sum of 11-13 = score of 4, and sum of 14-16 = score of 5 (range 1-5).

The total score is achieved by summing together the 5 domain scores and can therefore range between 5 (no pruritus) and 25 (most severe pruritus).

7.9.6.3 EQ-5D-5L

The EuroQoL 5 Dimensions, 5 levels (EQ-5D-5L) is a generic, multidimensional, health-related, quality-of-life instrument and comprises a Visual Analogue Scale (VAS) and a short descriptive system questionnaire.

The VAS records the subject's overall current health on a vertical VAS where the endpoints are labelled "(100) The best health you can imagine" and "(0) The worst health you can imagine." The VAS provides a quantitative measure of the subject's perception of his/her overall health.

The descriptive system questionnaire allows subjects to rate their health in 5 domains: mobility, self-care, usual activities, pain/discomfort, and anxiety/depression using a 5-level scale

indicating: 1. no problem, 2. slight problem, 3. moderate problem, 4. severe problem, or 5. unable to/extreme problems. The perceived problem levels for each domain are combined into a 5-digit health state that is converted to an index value, which reflects how good or bad a health state is according to the preferences of the general population with higher scores indicating better quality of life.

7.9.7 Subject's indication of CKD-aP treatment area size

The subject must indicate the size of the CKD-aP treatment area (by greying out all areas treated) at Baseline, Week 1, Week 4, Week 8, and Week 12 or Early Termination using the CKD-aP treatment area diagram below, if necessary, with assistance from trial staff. Subsequently, trial staff must estimate the size of the treatment area (in terms of % body surface area treated) based on the CKD-aP treatment area diagram:

CKD-aP treatment area diagram – according to subject (example)

7.10 Clinician-reported outcome (ClinRO) assessments

7.10.1 Identification of CKD-aP target area

At the Baseline visit a CKD-aP target area that fulfils the following criteria must be identified by trained clinical staff:

- The area must be among the areas with the worst CKD-aP according to the subject
- The area must measure minimum 10 cm x 10 cm in size (roughly the palm of a hand)
- The area must be easy for the subject to reach, to apply the IMP on and must be treated with the IMP throughout the double-blind treatment phase of the trial
- The area must not be in close proximity of dialysis access sites in haemodialysis subjects

When the CKD-aP target area has been identified it must be marked with a square on the "CKD-aP diagram." An example of a CKD-aP target area marked with an asterisk * is shown on the CKD-aP diagram below.

CKD-aP target area diagram (*example of CKD-aP target area)

7.10.2 Clinician's global assessment (CGA) of skin appearance

CGA of skin appearance on the entire body surface area must be evaluated by trained clinical staff (preferably the same staff member throughout the trial for an individual subject) and recorded in the eCRF at Screening, Baseline, Week 1, Week 4, Week 8, and Week 12 or Early Termination using a 5-point verbal rating scale (from clear to severe) as follows:

Please choose the description below that best describes the severity of skin dryness and skin signs of itch on the entire body surface area:

CGA score	Skin Dryness Description	Skin signs of Itch Description
Clear	No skin dryness	No active skin signs of itch* (chronic skin signs of itch may be present)
Almost clear	Barely perceptible skin dryness	Barely recognizable active skin signs of itch*
Mild	Easily perceptible skin dryness	Easily recognizable active skin signs of itch*
Moderate	Moderate [between Mild and Severe] skin dryness	Moderate [between Mild and Severe] active skin signs of itch*
Severe	Marked skin dryness	Marked active skin signs of itch*

*Active skin signs of itch include but are not necessarily limited too excoriation, crusting, superficial bleeding or intradermal bleeding (ecchymoses) or prurigo nodules and must be distinguished from chronic skin signs of itch, e.g., skin discoloration, thickening or scarring.

The overall CGA intensity is defined based on the intensity of the individual signs skin dryness and skin signs of itch. In case of difference in intensity of skin dryness and skin signs of itch then the worst intensity shall prevail in the overall CGA score (e.g., in case of mild skin dryness and severe skin signs of itch, then the overall CGA must be scored as severe).

7.10.3 Clinician's targeted assessment (CTA) of skin appearance

CTA of skin appearance in the CKD-aP target area (see Section 7.10.1 for description of CKDaP target area) must be evaluated by trained clinical staff (preferably the same staff member throughout the trial for an individual subject) and recorded in the eCRF at Baseline, Week 1, Week 4, Week 8, and Week 12 or Early Termination. CTA includes assessments of skin dryness and skin signs of itch and overall CTA in the CKD-aP target area using a 5-point verbal rating scale (from clear to severe) as follows:

Please choose the description below that best describes the skin dryness and skin signs of itch on the CKD-aP target area:

CTA score	Skin Dryness Description	Skin Signs of Itch Description
Clear	No skin dryness	No active skin signs of itch* (chronic skin signs of itch may be present)
Almost clear	Barely perceptible skin dryness	Barely recognizable active skin signs of itch*
Mild	Easily perceptible skin dryness	Easily recognizable active skin signs of itch*
Moderate	Moderate (between Mild and Severe) skin dryness	Moderate (between Mild and Severe) active skin signs of itch*
Severe	Marked skin dryness	Marked active skin signs of itch*

*Active skin signs of itch include but are not necessarily limited to excoriation, crusting, superficial bleeding or intradermal bleeding (ecchymoses), or prurigo nodules and must be distinguished from chronic skin signs of itch, e.g., skin discoloration, thickening, or scarring.

The overall CTA intensity is defined based on the intensity of the individual skin dryness and skin signs of itch assessments. In case of difference in intensity of skin dryness and skin signs of itch then the worst intensity shall prevail in the CTA score (e.g., in case of mild skin dryness and severe skin signs of itch, then the overall CTA must be scored as severe).

7.10.4 Imaging of CKD-aP

Imaging of the CKD-aP target area (see Section 7.10.1 for description of CKD-aP target area) will be obtained by the trained clinical staff at Baseline, Week 4, and Week 12 or Early Termination in a subset of subjects who provide additional consent. The same area must be used for imaging at the subsequent timepoints indicated in the SoA. Images must always be taken before skin tape stripping and skin biopsies.

The imaging procedure will be described in a separate manual. Steps will be taken to ensure that the identities of the subjects are protected. Additional informed consent will be obtained with regard to collection, transmission and use of images.

7.11 Biomarker assessments of CKD-aP

The subclinical effects of MC2-25 on CKD-aP will be evaluated by analyses of relevant biomarkers in skin biopsies and skin tape strips after completion of the trial.

Skin tape stripping provides information on biomarker changes in the most superficial layer of the skin, i.e., the stratum corneum, which is the uppermost part of the epidermis. In contrast, a skin biopsy can provide information on biomarker changes through all layers of the skin, i.e., the epidermis and the dermis. As this trial is the first in humans with the MC2-25 cream it is

important to understand not only whether the treatment has effects on biomarkers in the skin but also to understand to which skin depth such effects extend.

7.11.1 Skin biopsies

Skin biopsies will be obtained (at selected trial sites) by a physician at Baseline and Week 12 or Early Termination (after the Week 4 visit) in a subset of subjects who provide additional consent to have skin biopsies performed.

Skin biopsies will be taken from the upper right quadrant at the Baseline visit and from the upper left quadrant at the Week 12 (EoT or Early Termination) visit following the directions described in Section 7.10.1. Skin biopsies should be performed at a site without scratch marks and at least 2 cm apart.

Skin punch biopsies must be performed by trained staff under local anaesthesia using a disposable 4-mm puncher. The puncher is pushed into the skin by rotary movement until a "give away" feel is perceived. Suture is generally not needed. A cotton bandage is sufficient (Nischal 2008).

The skin biopsy specimens will be stored for relevant analyses of biomarkers of CKD-aP. The samples will be destructed within 1 year after trial completion.

7.11.2 Skin tape strips

Skin tape strips will be obtained by a physician at Baseline and Week 12 or Early Termination in all subjects.

Tape strips will be taken from the lower right quadrant at the Baseline visit and from the lower left quadrant at the Week 12 (EoT or Early Termination) visit following the directions described in Section 7.10.1.

Tape stripping is a minimally invasive technique to sequentially remove stratum corneum by repeated application of appropriate adhesive tape. Areas with, e.g., eczema and scratch marks should be avoided. Round adhesive tape discs are attached to the skin for 10 seconds using a disc pressure applicator. The tapes are gently removed with a tweezer and stored in closed plastic vials at room temperature at the site and during shipment. At the central laboratory the samples must be stored between -20°C and -30°C until analysis. The first strip is discarded, and the following are stored together in groups as follows: strips 2-4, strips 5-7, and strips 8-10 (Kezic 2011).

The skin tape strips will be stored for relevant analyses of biomarkers of CKD-aP. The samples will be destructed within 1 year after trial completion.

7.12 Adverse events

7.12.1 Adverse events assessments

The investigator or designee is responsible for obtaining, assessing, and documenting all AEs during the trial.

An AE is any untoward medical occurrence in a patient or clinical investigation subject administered an investigational or non-investigational medicinal product and which does not necessarily have to have a causal relationship with this treatment. An AE can therefore be any unfavourable and unintended sign (including an abnormal laboratory finding, for example), symptom, or disease temporally associated with the use of a medicinal product, whether or not considered related to the medicinal product.

All AEs will be documented in the eCRF, including a description of each AE, AE relationship to IMP administration, start and stop dates, seriousness, severity, action taken and outcome.

Any AE that meets the serious criteria must be reported as an SAE to PharmaLex (PLX) within 24 hours of first awareness.

Contact information:

Company: PharmaLex A/S, [name]

E-mail: [contact]

Throughout the trial, the occurrence of AEs should be monitored by nondirective questioning of the subject at each visit. Information on AEs can also be obtained from signs and symptoms detected during examinations, observations made by the trial site personnel, or spontaneous reports from subjects. Pre-existing conditions that worsen during the trial should also be recorded as AEs. This will also include worsening of the disease as judged by the investigator.

AEs requiring therapy must be treated in accordance with recognised standards of medical care to protect the health and well-being of the subject. Treatment due to an AE will be recorded in the subject's records and on the appropriate eCRF.

7.12.2 Reporting of adverse events

Adverse event information will be collected from individual trial subjects from signature of the informed consent form until the last trial visit.

If the event is reported as an SAE, the timelines for SAE reporting apply (see Section 7.12.10). If the event is reported as non-serious AE, it should be reported on the appropriate eCRF page.

All SAEs and related non-serious AEs must be followed by the investigator until they are resolved or until judged by the investigator to be stable/needing no further follow-up. All

relevant follow-up information will be reported in the eCRF (and to PharmaLex if it qualifies as an SAE, see Section 7.12.1).

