	Risk Mitigation: The first IMP application will be performed in the clinic. Adverse events will be evaluated more frequently during the first 2 weeks of the trial treatment phase (weekly) compared to the subsequent weeks of the trial treatment phase (bi-weekly). In addition, a subject may withdraw from the trial or discontinue trial treatment at any time at his/her own request or at the discretion of the investigator due to unacceptable adverse events.				
Risk Title: Use during Pregnancy	Risk Description: The toxicological profile of the active product ingredient Ala-Gln has been evaluated as part of the approval of Dipeptiven [®] with no indications of teratogenic or other embryotoxic and peri-postnatal injuries observed up to an intravenous dosage of 1.6 g N(2)-L-alanyl-L-glutamine/kg body weight per day. Reproductive toxicity studies have not been conducted with MC2-25 cream.				

Table 1: Summary of Risks and Mitigation Strategies

	-	
	Risk Mitigation: According to the SmPC Dipeptiven [®] should not be administered during pregnancy due to lack of experience. Therefore, female subjects can only be randomized in the trial if they are of either non-childbearing potential or of childbearing potential and have a negative pregnancy test at the Baseline visit and use a highly effective method of contraception throughout the trial (see inclusion criteria for details). Due to the short half-life in plasma (<5 min), pregnancy testing is only mandatory while subjects receive double-blind treatment.	
Trial Procedures		
Risk Title: Blood sampling	Risk Description: Blood sampling is invasive and there is always a slight risk of bruising, infections, pain, etc.	
	Risk Mitigation: All blood sampling will be performed by trained staff and the volume of blood to be drawn at each occasion is small (approximately 10 mL).	
Risk Title: Tape stripping	Risk Description: Repeated tape stripping may lead to transient, minor redness and irritation at the (~4 cm ²) tape stripping site.	
	Risk Mitigation: If unacceptable redness and or irritation develops during the procedure, the procedure must be stopped.	
Risk Title: Skin biopsies	Risk Description: As is the case with all invasive procedures, punch skin biopsies carry a small risk of bleeding and infection. In addition, a small scar may develop (Nischal 2008).	

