Diary (Handout)	Х	Х	Х		Х		Х			
Biopsy ¹⁵		Х							Х	
Tape stripping ¹⁶		Х							Х	
Prior & concomitant therapies ¹⁷	Х	Х	Х	Х	Х	Х	Х	Х	Х	Х
Adverse events		Х	Х	Х	Х	Х	Х	Х	Х	Х
Investigational medicinal product (IMP) dispensation		Х			Х		Х			
IMP return, compliance and accountability					Х		Х		Х	
IMP application ¹⁸				_	Х					
Diary (Review)		Х	Х		Х		Х		X	

- 1. Follow-up (FU) visit is only applicable if there are ongoing serious adverse events (SAEs) or related adverse events (AEs) at Week 12. (X) indicates assessments to be performed if judged necessary by the investigator.
- 2. An unscheduled visit can be conducted to perform any of the postbaseline assessments or procedures included in the SoA if deemed necessary by the Investigator.
- 3. In the case of trial withdrawal or treatment discontinuation, all assessments of the Week 12 (End of Treatment [EoT]) visit have to be performed. The end of treatment form must be completed when treatment is discontinued and the end of trial form must be completed at end of the trial or in case of trial withdrawal.
- 4. Phone calls: To remind subjects about diary documentation (in particular once-daily WI-NRS assessments that must be performed for 8 days leading up to each on-site visit [i.e., from day -7 to day 0 where day 0 = next on-site visit day]) and to ask for AEs. Phone visits may be replaced by in-clinic visits where relevant, e.g., in subjects going to the dialysis unit for haemodialysis.
- 5. Informed consent must be signed by both subject and investigator before any trial-related procedures are performed.

Clinical Trial Protocol

Protocol No. MC2-25-C1 Vers.3.0 EU/30-Nov-2022

- 6. At-home (diary) assessments must be performed for 8 days leading up to each visit, i.e., from day -7 to day 0 where day 0 = next on-site visit day.
- 7. The WI-NRS must also be reported by the subject at on-site visits
- 8. At all on-site visits, all patient-reported outcome (PRO) assessments should be completed before all other clinical assessments or procedures.
- 9. The trial staff must estimate the % body surface area treated based on the subject's indication of CKD-aP treatment area size on the CKD-aP treatment area diagram.
- 10. Physical exam: A complete physical examination is required at Screening and Week 12 (EoT or Early Termination) visits. An abbreviated physical examination is required at the Baseline visit (and if judged necessary by the investigator) at the FU visit if the FU visit is applicable.

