7.12.4 Relationship of adverse events to trial treatment

The investigator is responsible for assessing the relationship of an AE to the IMP treatment using good clinical judgment and the following definitions:

- Not related The AE is clearly explained by another cause not related to the IMP administration; the temporal relationship of the AE to IMP administration makes a causal relationship clearly improbable or concomitant medication, therapeutics interventions, or underlying condition provide a sufficient explanation for the observed AE.
- Unlikely related The AE is most likely related to actiology other than the IMP administration; the temporal relationship of the AE to IMP administration makes a causal relationship unlikely, and other concomitant medication, therapeutic interventions or underlying disease provide plausible explanations for the observed AE.
- Possibly related The AE and administration of IMP are temporally related, but the AE can be explained equally well by causes other than the IMP administration. A causal relationship is conceivable and cannot be dismissed.
- Probably related The AE and use of IMP are temporally related, and the AE is more likely explained by IMP administration than by other causes. Good reason and sufficient documentation to assume a causal relationship.

The last relationship recorded during the course of an AE will be considered the final relationship as the investigator is assumed to have had the most information to perform the relationship assessment at that time.

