7.12.9 Serious adverse event

An SAE is any untoward medical occurrence that at any dose:

- Results in death
- Is life-threatening

- Requires in-patient hospitalisation or prolongation of existing hospitalisation
- Results in persistent or significant disability/incapacity
- Is a congenital anomaly/birth defect
- Other serious or important medical event

Any medical important events that may not result in death, be life-threatening, or require hospitalisation may be considered an SAE when, based on appropriate medical judgment, they may jeopardise the subject or the subject may require medical or surgical intervention to prevent one of the outcomes listed in the above definitions.

The death of a subject enrolled in a trial is per se not an event, but an outcome. Any event resulting in a fatal outcome must be fully documented and reported, regardless of the causality relationship to the IMP.

Any pre-planned hospitalisations that are known at the time of signing the informed consent form will not be recorded as SAEs, however they will be recorded as AEs only.

Any SAE, whether or not deemed IMP-related or expected, must be reported immediately to PharmaLex as soon as it becomes known to the investigator and not later than within 24 hours of his/her knowledge of the occurrence of an SAE (see Section 7.12.10). The investigator will document such events in the best possible detail on the SAE Report Form.

A suspected unexpected serious adverse reaction (SUSAR) is an SAE that is both unexpected (not listed in the Reference Safety Information (RSI) section of the IB, and for which there is evidence to suggest a causal relationship between the drug and the SAE. The Institutional Review Board (IRB)/Independent Ethics Committee (IEC) will be informed of SUSARs according to local requirements. All investigators participating in the trial will also be notified of SUSARs.

Investigator instructions for reporting SAEs are provided in Section 7.12.10.

SAEs occurring after a subject has completed the trial and deemed IMP-related by the investigator should be reported to the sponsor if the investigator becomes aware of them.

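### In the optional biopsy subset, subjects with no qualifying event ongoing at Week 12 have no planned adverse event contact after the second biopsy

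*Protocol*

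**What the plan says.** - **When biopsies are taken.** Protocol 7.11.1: "Skin biopsies will be obtained (at selected trial sites) by a physician at Baseline and Week 12 or Early Termination". They are limited to a subset who give additional consent, and an early-termination biopsy applies only after the Week 4 visit. The schedule in SAP Table 1 is the same.
- **The named risk.** Protocol Table 1 (Section 2.3): "punch skin biopsies carry a small risk of bleeding and infection"; it adds that a small scar may develop. The mitigation listed is sterile conditions, trained staff, separate consent, information about the risks, and exclusion of subjects with bleeding disorders or anaesthetic hypersensitivity. It lists no check after the procedure.
- **When collection ends.** Protocol 7.12.2: "Adverse event information will be collected from individual trial subjects from signature of the informed consent form until the last trial visit".
- **Who has a visit after Week 12.** Protocol Table 3, footnote 1: "Follow-up (FU) visit is only applicable if there are ongoing serious adverse events (SAEs) or related adverse events (AEs) at Week 12".
- **What relatedness refers to.** Protocol 7.12.4: "The investigator is responsible for assessing the relationship of an AE to the IMP treatment". No category covers a relationship to a trial procedure.
- **After completion.** Protocol 7.12.9: "SAEs occurring after a subject has completed the trial and deemed IMP-related by the investigator should be reported to the sponsor", and then only if the investigator becomes aware of them.

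**The concern.** The second biopsy coincides with the visit at which adverse event collection normally closes. A complication that has not yet appeared at that visit cannot be ongoing there, so it cannot trigger the conditional Week 14 visit. The rules that might otherwise catch it are tied to the IMP. The duty in 7.12.2 to follow events to resolution covers serious events and related non-serious events, and the post-completion rule in 7.12.9 covers only serious events attributed to the IMP.

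What is at stake is how completely the trial records a harm of its own invasive procedure, which the sponsor names in Table 1. Section 2.3 describes the population as generally frail. Exclusion criterion 8 lets subjects with suspected uremic platelet dysfunction, without other bleeding diatheses, be enrolled if the investigator agrees. Section 7.11.1 expects the wound to be left without a suture in general. A serious bleed or infection after the last visit, judged unrelated to the cream, would carry no reporting duty under 7.12.9.

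**Working it through.** **1. Reproduce the stated trial duration.** The inputs are the day grid in Protocol Table 3: screening up to 28 days, treatment 84 days, conditional follow-up 14 days after end of treatment.

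28 + 84 + 14 = 126 days; 126 / 7 = 18.0 weeks.

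This matches the 18-week maximum in Section 4.1. The stated maximum therefore already contains the Week 14 slot. With the +4 day window at Week 12 and the +2 day window at follow-up the total is 132 days (132 / 7 = 18.9 weeks), so 18 weeks is a nominal figure.

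**2. Observation after the Baseline biopsy (day 0).** The adverse event row of Table 3 is marked on days 7, 14, 28, 42, 56, 70 and 84.

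Planned contacts = 7. Planned observation = 84 − 0 = 84 days, or 80 to 88 days with the ±4 day window at Week 12.

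**3. Observation after the Week 12 biopsy (day 84).**

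| Subject | Last planned contact | Planned days after biopsy | Planned contacts |
|---|---|---|---|
| No serious or related event ongoing at Week 12 | Day 84 | 84 − 84 = 0 | 0 |
| Qualifies for Week 14 | 14 days after end of treatment | 14 (12 to 16 with the ±2 day window) | 1 |

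**4. How many fall in the first row.** The documents give no rate for qualifying. Call the share who qualify f; the share with no planned contact is 1 − f, and the mean planned observation is 14 × f days. As an assumption, f = 5% gives 95% with none and a mean of 0.7 days; f = 30% gives 70% with none and a mean of 4.2 days. The first row is the majority for any f below 50%. That it is the majority is an inference, although the protocol does write Week 14 as the exception.

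**5. Other routes by which a delayed complication might be recorded.**

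- *Seen during the Week 12 visit.* It can be recorded. Section 7.1 requires only that the biopsy follow imaging and the targeted skin assessment, not that it be the last step.
- *Unscheduled visit (Table 3, footnote 2).* It is possible at the investigator's discretion. The footnote does not say whether it applies after Week 12, and it is not a planned search for events.
- *Early treatment discontinuation.* End-of-treatment assessments are done when treatment stops, and Section 5.4 encourages attendance at the remaining visits, so later contacts may follow.
- *Post-completion rule (7.12.9).* It covers serious, IMP-related events only, and only if they become known.

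None of these is a planned contact for a subject who completes 12 weeks with no qualifying event.

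**The case against.** The strongest case against is about scope. Biopsy is optional, done at selected sites and separately consented. Bleeding risk is limited by exclusion criteria 8 and 19 and by the anticoagulation rule in 6.7.2. The same procedure at Baseline is followed by seven contacts and a complete physical examination at Week 12, so the trial does observe biopsy complications. The safety objective compares cream with vehicle, and SAP 6.2 removes the biopsy biomarker analysis. All of this stands and keeps the point minor. It does not supply a contact after the second biopsy, which SAP Table 1 still schedules.

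A reader might also infer more than the documents support:

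- *That half of all procedures, tape stripping included, go unobserved.* All subjects are tape-stripped twice, so 108 × 2 = 216 sessions, of which up to 108 fall at Week 12 or end of treatment. But Table 1 describes the effect as transient and minor and tells staff to stop if it becomes unacceptable during the procedure. Most of it should be visible in clinic, so a count of sessions does not measure missed harm.
- *That a biopsy complication can never trigger follow-up.* Any ongoing serious event triggers Week 14, whatever its cause. Protocol 8.7.1 and SAP 5.6.4 count an unlikely relationship as related. These are analysis definitions, but they are the only text saying which ratings count, and an event in the IMP-treated target area could receive such a rating.
- *That a number of missed events can be given.* The documents state neither the number of subjects biopsied nor a complication rate.
- *That procedure harms cannot be told apart from application-site reactions.* Procedure sites are fixed by quadrant (7.11.1, 7.11.2), each event has a description and start date (7.12.1), and the definitions in 7.12.4 already allow therapeutic interventions as an alternative cause. Tape stripping applies equally to both arms. The eCRF is not among the documents, so the absence of a procedure-relationship item is shown for the protocol text only.

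**Conclusion.** The point holds for subjects in the optional biopsy subset who have no serious or related adverse event ongoing at Week 12. For them the plan provides 84 nominal days and seven contacts after the first biopsy, and no planned contact after the second. A delayed bleed or infection could go unrecorded, and a serious one after completion is reportable only if attributed to the IMP.

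The conclusion rests on reading the last trial visit as the last planned visit, and on the premise that some biopsy complications appear after the subject has left the clinic; the documents do not state their timing. Tape stripping is not a material part of the gap. The effect is on completeness of safety recording in a subset whose size is not given. The primary analysis, the sample size and the between-arm conclusions are unaffected. Severity is minor: a cheap improvement.

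**What to change.** 1. In Protocol 7.12.2 and Table 3, extend adverse event collection for subjects biopsied at Week 12 or end of treatment to one phone contact in the existing Week 14 slot. Ask the same of subjects biopsied at early termination, if they agree. State that this contact closes collection for them, and mirror the change in SAP Table 1. It stays within the stated 18-week nominal maximum.
2. In Table 3 footnote 1, 7.12.2 and 7.12.9, widen the relatedness condition so that it covers events related to the IMP or to a trial procedure.
3. Optionally, add an item for relationship to biopsy or tape stripping beside the IMP relationship on the adverse event page. Under SAP 5.6.4 treatment emergence has no end date, so events found at the new contact would enter the treatment-emergent tables; the item would let them be identified there.

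The cost is protocol wording, one call per biopsied subject and, if item 3 is adopted, one eCRF field. A few more events unrelated to the IMP will be reported, and item 2 may add an occasional Week 14 visit.
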